**Table KGAD.6.9. Description of Efficacy/Health Outcome Analyses**

Measure	Variable	Analysis Method (Section 6.1)	Population (Section 6.1.1)	Comparison/Time Point	Analysis Type
Investigator’s Global Assessment (IGA)	Proportion of patients achieving IGA [0,1] with a $\geq 2$ -point improvement	CMH analysis with MCMC-MI	mITT	Leb 250 mg Q2W vs PBO; Week 16 and all scheduled visits in Treatment Period	Primary analysis: W16; Secondary analysis: other timepoints
		CMH analysis with NRI	mITT	Leb 250 mg Q2W vs PBO; Week 16 and all scheduled visits in Treatment Period	Supplementary analysis
		CMH analysis with tipping point analysis	mITT	Leb 250 mg Q2W vs PBO; Week 16	Sensitivity analysis
	Proportion of patients achieving IGA [0]	CMH analysis with NRI	mITT	Leb 250 mg Q2W vs PBO; Week 16 and all scheduled visits in Treatment Period	Secondary analysis
	Proportion of patients achieving both IGA [0,1] with a $\geq 2$ -point improvement and a $\geq 4$ -point improvement in Pruritus Numeric Rating Scale (NRS)	CMH analysis with MCMC-MI	mITT with Baseline Pruritus NRS score at least 4	Leb 250 mg Q2W vs PBO; Week 16 and all scheduled visits in Treatment Period	Secondary analysis
CMH analysis with NRI		mITT with Baseline Pruritus NRS score at least 4	Leb 250 mg Q2W vs PBO; Week 16 and all scheduled visits in Treatment Period	Secondary analysis	
Eczema Area and Severity Index (EASI)	Change from baseline in EASI score	ANCOVA with MCMC-MI	mITT	Leb 250 mg Q2W vs PBO; Week 16 and all scheduled visits in Treatment Period	Secondary analysis: percent change Week 16
	Percent change from baseline in EASI score	MMRM	mITT	Leb 250 mg Q2W vs PBO; Week 16 and all scheduled visits in Treatment Period	Secondary analysis

Description of Efficacy/Health Outcome Analyses

Measure	Variable	Analysis Method (Section 6.1)	Population (Section 6.1.1)	Comparison/Time Point	Analysis Type
	Proportion of patients achieving EASI-75	CMH analysis with MCMC-MI	mITT	Leb 250 mg Q2W vs PBO; Week 16 and all scheduled visits in Treatment Period	Primary analysis: EASI-75, W16; Secondary analysis: EASI-90, W16; Secondary analysis: other timepoints
	Proportion of patients achieving EASI-90				
	CMH analysis with NRI				
		CMH analysis with tipping point analysis	mITT	Leb 250 mg Q2W vs PBO; Week 16	Sensitivity analysis
	Proportion of patients achieving EASI-50	CMH analysis with MCMC-MI	mITT	Leb 250 mg Q2W vs PBO; Week 16 and all scheduled visits in Induction Period	Secondary analysis
	Proportion of patients achieving both EASI-75 and a $\geq 4$ -point improvement in Pruritus NRS	CMH analysis with MCMC-MI	mITT with Baseline Pruritus NRS score at least 4	Leb 250 mg Q2W vs PBO; Week 16 and all scheduled visits in Treatment Period	Secondary analysis
	CMH analysis with NRI	mITT with Baseline Pruritus NRS score at least 4	Leb 250 mg Q2W vs PBO; Week 16 and all scheduled visits in Treatment Period	Secondary analysis	
Body Surface Area (BSA) Affected by AD	Change from baseline in BSA score	MMRM	mITT	Leb 250 mg Q2W vs PBO; Week 16 and all scheduled visits in Treatment Period	Secondary analysis

Description of Efficacy/Health Outcome Analyses

Measure	Variable	Analysis Method (Section 6.1)	Population (Section 6.1.1)	Comparison/Time Point	Analysis Type
Pruritus Numeric Rating Scale (NRS)	Change from baseline in Pruritus NRS	ANCOVA with MCMC-MI	mITT	Leb 250 mg Q2W vs PBO; Week 16 and all scheduled visits in Treatment Period	Secondary analysis:
	Percent Change from baseline in Pruritus NRS score	MMRM	mITT	Leb 250 mg Q2W vs PBO; Week 16 and all scheduled visits in Treatment Period	Secondary analysis
	Proportion of patients achieving at least 4-point improvement in pruritus NRS in patients who had baseline pruritus NRS $\geq 4$	CMH analysis with MCMC-MI	mITT with Baseline Pruritus NRS score at least 4	Leb 250 mg Q2W vs PBO; Week 16 and all scheduled visits in Treatment Period	Secondary analysis: Weeks 1, 2, 4, and 16; Secondary analysis: other timepoints
		CMH analysis with NRI	mITT with Baseline Pruritus NRS score at least 4	Leb 250 mg Q2W vs PBO; Week 16 and all scheduled visits in Treatment Period	Supplementary analysis
		CMH analysis with tipping point analysis	mITT with Baseline Pruritus NRS score at least 4	Leb 250 mg Q2W vs PBO; Weeks 1, 2, 4, and 16	Sensitivity analysis
Sleep-loss Score	Percent Change from baseline in Sleep-loss Change from baseline in Sleep-loss	ANCOVA with MCMC-MI	mITT	Leb 250 mg Q2W vs PBO; Week 16 and all scheduled visits in Treatment Period	Secondary analysis: percent change, W16; Secondary analysis: other timepoints
		MMRM			
	Proportion of patients achieving at least 2-point improvement Sleep-loss in patients who had baseline Sleep-loss $\geq 2$	CMH analysis with MCMC-MI	mITT with Baseline Sleep-loss score at least 2	Leb 250mg Q2W vs PBO; Week 16 and all scheduled visits in Treatment Period	Secondary analysis: Weeks 16; Secondary analysis: other timepoints
CMH analysis with NRI		mITT with Baseline Sleep-loss score at least 2	Leb 250 mg Q2W vs PBO; Week 16 and all scheduled visits in Treatment Period	Secondary analysis: Weeks 1, 2, 4, and 16; Secondary analysis: other timepoints	

Description of Efficacy/Health Outcome Analyses

Measure	Variable	Analysis Method (Section 6.1)	Population (Section 6.1.1)	Comparison/Time Point	Analysis Type
(Children) Dermatology Life Quality Index (DLQI/CDLQI)	Change from baseline in DLQI total Score	ANCOVA with MCMC-MI  MMRM	mITT	Leb 250 mg Q2W vs PBO; Week 16 and all scheduled visits in Treatment Period	Secondary analysis: W16 for DLQI change; Secondary analysis: other timepoints
	Proportion of patients achieving at least 4-point improvement in DLQI in patients who had baseline DLQI score $\geq 4$	CMH analysis with MCMC-MI NRI	mITT	Leb 250 mg Q2W vs PBO; Week 16 and all scheduled visits in Treatment Period	Secondary analysis: W16 for DLQI change; Secondary analysis: other timepoints
	Change from baseline in CDLQI Score	MMRM	mITT	Leb 250 mg Q2W vs PBO; Week 16 and all scheduled visits in Treatment Period	Secondary analysis
SCORing Atopic Dermatitis (SCORAD)	Change from baseline in SCORAD score	ANCOVA with LOCF	mITT	Leb 250 mg Q2W vs PBO; Week 16 and all scheduled visits in Treatment Period	Secondary analysis
	Percent change from baseline in SCORAD score				
	Proportion of patients achieving SCORAD75	CMH analysis with NRI	mITT	Leb 250 mg Q2W vs PBO; Week 16 and all scheduled visits in Treatment Period	Secondary analysis
	Proportion of patients achieving SCORAD90				
Patient-Oriented Eczema Measure (POEM)	Change from baseline in POEM score	MMRM	mITT	Leb 250 mg Q2W vs PBO; Week 16 and all scheduled visits in Treatment Period	Secondary analysis
European Quality of Life-5 Dimensions-5 Levels (EQ-5D-5L)	Proportion of patients having no problem in each domain: 
 
EQ-5D mobility
 
EQ-5D self-care
 
EQ-5D usual activities
 
EQ-5D pain/ discomfort
 
EQ-5D anxiety/ depression
 
	CMH analysis with NRI	mITT	Leb 250 mg Q2W vs PBO; Week 16	Secondary analysis

Description of Efficacy/Health Outcome Analyses

Measure	Variable	Analysis Method (Section 6.1)	Population (Section 6.1.1)	Comparison/Time Point	Analysis Type
	Change from baseline in 
 
• EQ-5D VAS
 
• EQ-5D-5L UK Population-based index score
 
• EQ-5D-5L US Population-based index score
 
	ANCOVA with LOCF	mITT	Leb 250 mg Q2W vs PBO; Week 16	Secondary analysis
Patient-Reported Outcomes Measurement Information System (PROMIS®)	Change from baseline in PROMIS Anxiety score  Change from baseline in PROMIS Depression score	ANCOVA with LOCF	mITT	Leb 250 mg Q2W vs PBO; Week 16	Secondary analysis
Asthma Control Questionnaire (ACQ-5)	Change from baseline in ACQ-5 score	ANCOVA with LOCF	mITT with self-reported comorbid asthma	Leb 250 mg Q2W vs PBO; Week 16	Secondary analysis
Topical corticosteroid (TCS) or topical calcineurin inhibitor (TCI) Use	Time (days) to TCS / TCI-free use from Baseline to Week 16	KM method with log-rank test	mITT	Leb 250 mg Q2W vs PBO;	Secondary analysis
	Proportion of TCS/TCI free days from Baseline to Week 16	MMRM	mITT	Leb 250 mg Q2W vs PBO; Week 16 and all scheduled visits	Secondary analysis

**Description of Efficacy/Health Outcome Analyses**

Modified Subcutaneous Administration Assessment Questionnaire (SQAAQ)	Proportion of patients who answer “Strongly Agree” or “Agree” in each of 10 questions in a visit	Observed case	Patients who complete SQAAQ at any visit	Leb 250 mg Q2W vs PBO; by sequence of each self/caregiver injection; (note, patient could start self/caregiver injection at any visit, the visits will be aligned as: 1st self/caregiver injection, 2nd self/caregiver injection,...)	Secondary analysis
---	--	---------------	--	---	--------------------

Abbreviations: AD =atopic dermatitis; ANCOVA = analysis of covariance; CMH = Cochran-Mantel-Haenszel; KM = Kaplan-Meier; Leb = lebrikizumab; LOCF = last observation carried forward; MCMC-MI = Markov chain Monte Carlo multiple imputation; mITT = modified intent-to-treat; MMRM = mixed-model repeated measures; NRI = nonresponder imputation; PBO = placebo; Q2W = every 2 weeks; VAS = Visual Analog Scale; W = week.

### **6.11.1. Primary Outcome and Methodology**

The primary analysis of the study is to test the null hypotheses that lebrikizumab 250 mg Q2W is the same as placebo when evaluating the proportion of patients achieving IGA of 0 or 1 at Week 16 in the mITT Population. For EMA, an additional null hypothesis is that lebrikizumab 250 mg Q2W is the same as placebo when evaluating the proportion of patients achieving EASI-75 at Week 16 in the mITT Population.

The primary estimand for the primary analysis is described in Section 6.2.1. The missing values will be imputed using MCMC-MI based on missing at random assumption (Section 6.4.1).

A CMH test as described in Section 6.1.2 will be used for the comparisons. The odds ratio, the corresponding 95% CIs and p-value, as well as the treatment differences and the corresponding 95% CIs, will be reported.

Multiplicity controlled analyses will be performed on the primary and major secondary objectives to control the overall Type I error rate at a 2-sided alpha level of 0.05. A gatekeeping approach will be used to perform the multiplicity controlled analyses as described in Section 6.6.

Primary outcome IGA 0/1 and EASI-75 and their analysis are described in [Table KGAD.6.8](#) and [Table KGAD.6.9](#).

### **6.11.2. Sensitivity Analyses of Primary Outcome**

Sensitivity analyses are included to demonstrate robustness of analyses methods using different missing data imputations, populations and analyses assumptions. Sensitivity analyses for primary outcomes include the tipping point analysis based on missing not at random assumption (Section 6.4.2).

Secondary analyses for both primary and secondary endpoints are described [Table KGAD.6.8](#) and [Table KGAD.6.9](#).

There will be no adjustment for multiple comparisons for additional analyses of the primary outcome.

### **6.11.3. Major Secondary Efficacy Analyses**

Major secondary outcomes and their analyses are described in [Table KGAD.6.8](#) and [Table KGAD.6.9](#).

### **6.11.4. Other Secondary Efficacy Analyses**

Other secondary outcomes and their analyses are described in [Table KGAD.6.8](#) and [Table KGAD.6.9](#).

## **6.12. Health Outcomes/Quality-of-Life Analyses**

Analyses of POEM, DLQI, EQ-5D-5L, PROMIS, and ACQ-5 are described in [Table KGAD.6.8](#) and [Table KGAD.6.9](#).

### 6.13. Bioanalytical and Pharmacokinetic/Pharmacodynamic Methods

Details of pharmacokinetic (PK)/pharmacodynamic (PD) analyses can be found in a separate PK/PD analysis plan.

### 6.14. Safety Analyses

The planned analyses of safety data will be performed with an intent to maintain consistency with compound level standard safety analyses (PSAP). These standards are based on internal standards which were informed by Clinical Data Interchange Standards Consortium (CDISC) standards, regulatory guidance (for example, FDA Clinical Review Template), and cross-industry standardization efforts (for example, Pharmaceutical Users Software Exchange [PhUSE] white papers from the Standard Analyses and Code Sharing Working Group provided in the PhUSE Computational Science Deliverables Catalog).

Safety evaluations will be based on the Modified Safety Population (Treatment Period). A sensitivity analysis will also be conducted on the Safety Population (Treatment Period).

Analysis populations are fully defined in [Table KGAD.6.1](#) while [Table KGAD.6.2](#) describes the treatment groups and the comparisons for each analysis population.

For document writing purposes for safety, tests with two-sided p-values less than 0.05 will be referred to as having strong statistical evidence for a treatment difference, unless otherwise noted. However, p-values should not be over-interpreted for these safety analyses. Except for pre-specified hypotheses, they correspond to data-driven hypotheses and hence are only useful as a flagging mechanism.

Not all displays described in this section will necessarily be included in the CSRs. Any display described and not provided in the CSR would be available upon request. Not all displays will necessarily be created as a “static” display. Some may be incorporated into interactive display tools instead of or in addition to a static display. Any display created interactively will be included in the CSR if deemed relevant to the discussion.

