1.3.1.1. Summary of Study GS29250 (TREBLE)

Study Design

TREBLE was a Phase 2, global, randomized, double-blind, placebo-controlled trial designed to evaluate the safety and efficacy of lebrikizumab in adult patients (18–75 years of age) with persistent moderate to severe AD, inadequately controlled by TCS. The study consisted of 3 study periods: a run-in period (2 weeks), a treatment period (12 weeks), and a safety follow-up period (8 weeks). Patients applied emollient at least once daily and TCS of medium potency to all active skin lesions twice daily through the study. A total of 212 patients were randomized as follows: 53 to the lebrikizumab 250 mg, single dose group; 53 to the lebrikizumab 125 mg, single dose group; 52 to the lebrikizumab 125 mg Q4W group; and 54 to the placebo Q4W group.

Efficacy Results

- EASI-50 at Week 12 (primary endpoint) was achieved by patients treated with lebrikizumab 125 mg Q4W, with a treatment difference between this group and placebo) of 20.1% ($p = 0.0261$).
- Lebrikizumab 125 mg Q4W group demonstrated statistically significant differences from placebo in EASI-75 and SCORAD-50 and adjusted mean change from baseline to Week 12.

Safety Results

- Injection-site reactions occurred infrequently (1.3% all lebrikizumab treated vs. 1.9% placebo); all events were non-serious, lasted a median of 1 to 3 days, and did not lead to treatment discontinuation or interruption.
- Herpes viral infections and zoster occurred infrequently, but only among lebrikizumab-treated patients (6 of 156 [3.8%]); all events were non-serious, and none led to treatment discontinuation or dose interruption of lebrikizumab.
- Eosinophil-associated adverse events (AEs) were reported infrequently, but only occurred among lebrikizumab-treated patients (3.2%); however, all events were non-serious, did

not result in interruption of treatment, and there were no other associated clinical symptoms noted.

- Allergic conjunctivitis events were only reported in lebrikizumab-treated patients (8 of 156 patients [5.1%] vs. 0% in placebo treated patients); all events were non-serious, did not lead to treatment discontinuation, all events recovered or resolved, and all patients had a history of asthma. Imbalances in allergic conjunctivitis events were not reported in previous lebrikizumab trials.

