1.3.1.3. Summary of Dose Ranging Study DRM06-AD01

Study Design

DRM06-AD01 was a Phase 2b, randomized, double-blind, placebo-controlled, dose-ranging study to evaluate the safety and efficacy of lebrikizumab in adult patients with moderate to severe AD. A total of 280 patients were randomized to 1 of 4 treatment groups (in a 3:3:3:2 ratio): 73 to lebrikizumab 125 mg Q4W (with a loading dose of 250 mg); 80 to lebrikizumab 250 mg Q4W (with a loading dose of 500 mg); 75 to lebrikizumab 250 mg Q2W (with a loading dose of 500 mg given at baseline and Week 2); 52 to placebo Q2W.

Efficacy Results

- Statistically significantly greater proportions of patients in each of the lebrikizumab 250 mg Q4W and 250 mg Q2W groups achieved EASI-50, EASI-75, or EASI-90 at Week 16 than the placebo group.
- A statistically significantly greater proportion of patients in each of the lebrikizumab 250 mg Q4W and 250 mg Q2W groups had both an IGA score of 0 or 1 and a ≥ 2 -point improvement in IGA score at Week 16 than the placebo group.
- The lebrikizumab 250 mg Q2W group had a statistically significantly greater proportion of patients who achieved a ≥ 4 -point improvement in pruritus NRS compared with the placebo group.
- Positive changes in pruritus correlated with positive changes in sleep; the lebrikizumab 250 mg Q4W and 250 mg Q2W groups had statistically significant percent reductions in sleep loss due to itching compared with placebo ($p=0.0459$ and $p=0.0062$, respectively).

Safety Results

- The incidences of conjunctivitis (2.6% all lebrikizumab groups, 0 placebo), herpes infections (2.2% all lebrikizumab groups, 0 placebo), and herpes zoster (0.9% all lebrikizumab groups, 0 placebo) were relatively low.
- Three patients (1.3%) in the lebrikizumab groups and 2 patients (3.8%) in the placebo group had an SAE. Those reported in the lebrikizumab groups were severe chest pain (1 patient in the 250 mg Q2W group), femur fracture of moderate severity (1 patient in the 125 mg Q4W group), and panic attack of moderate severity (1 patient in the 250 mg Q2W group). Those reported in the placebo group were severe chronic obstructive

pulmonary disease, severe edema peripheral, and severe pulmonary embolism. All SAEs were considered by the investigator as not related to study drug.

- Most AEs were considered not related to study drug; those considered related were reported for 16.2% of patients in the lebrikizumab groups and 5.8% of patients in the placebo group

Conclusions

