For variables that are not collected at each postbaseline visit, data may exist at visits where the variable was not scheduled to be collected. In these situations, data from the early discontinuation visit that do not correspond to the planned collection schedule will be excluded from the MMRM analysis (Andersen and Millen 2013). Also for by-visit summaries/displays such as boxplots, the weeks when data was not scheduled to be collected may not be displayed. However, unscheduled assessments within any defined study period will still be used in the shift analyses, and for imputing values for the change from baseline to last observation carried forward (LOCF) endpoint analyses.

The Kaplan-Meier (KM) product limit method may be used to estimate the survival for time to event analyses. The log-rank test stratified by the stratification factors mentioned in Section 6.3 will be reported. A Kaplan-Meier plot of the time to event by treatment group may be provided.

Unless specified otherwise, Fisher's exact test will be used for adverse events (AEs) and other categorical safety measures. Odds ratios will be created with lebrikizumab treatment as the numerator, and placebo as the denominator. Continuous vital sign and laboratory values will be analyzed by an ANCOVA with treatment and baseline value in the model.

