**Table KGAD.6.10. Summary Tables/Listings Related to Adverse Events**

Analysis	Population (Section 6.1.1)
Overview of AEs	Modified Safety; Safety (sensitivity analysis)
Summary of TEAE by PTs	Modified Safety; Safety (sensitivity analysis)
Summary of TEAE by PTs occurring in $\geq 1\%$ of patients	Modified Safety; Safety (sensitivity analysis)
Summary of TEAE possibly related to study drug by PTs within SOC	Modified Safety; Safety (sensitivity analysis)
Summary of TEAE by PTs within SOC	Modified Safety; Safety (sensitivity analysis)
Summary of TEAE PTs by maximum severity	Modified Safety; Safety (sensitivity analysis)
Summary of SAE by PT within SOC	Modified Safety; Safety (sensitivity analysis)
Summary of AEs leading to treatment discontinuation by PT with SOC	Modified Safety; Safety (sensitivity analysis)
Listing of SAEs (including Death)	ITT
Listing of primary AEs leading to study treatment discontinuation	ITT
Listing of TEAE (for Japan submission only)	Safety

Abbreviations: AE = adverse event; ITT = Intent-to-Treat;

PT = Preferred Term; SAE = serious adverse event; SOC = System Organ Class; TEAE = treatment-emergent adverse event.

Statistical comparisons will be performed using Fisher's exact test. Odds ratio will be provided.

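### The SAP compares adverse events between arms by a Fisher p-value and an odds ratio, with no stated interval or zero-cell rule; for conjunctivitis and herpes at Phase 2 rates the p<0.05 flag would usually stay silent

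*SAP*

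**What the plan says.** SAP 6.1.2 sets the default: "Unless specified otherwise, Fisher's exact test will be used for adverse events (AEs) and other categorical safety measures". The odds ratio there takes lebrikizumab over placebo. The note under Table KGAD.6.10 repeats this for the adverse event tables: "Statistical comparisons will be performed using Fisher's exact test. Odds ratio will be provided". SAP 6.14 adds that "tests with two-sided p-values less than 0.05 will be referred to as having strong statistical evidence for a treatment difference", and then qualifies it: "However, p-values should not be over-interpreted for these safety analyses", and such p-values "hence are only useful as a flagging mechanism".

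Neither 6.1.2, 6.14.2 nor 6.14.6 names a confidence interval, a risk difference or a rule for arms with no events. For binary efficacy endpoints, 6.1.2 asks for a stratified risk difference and an odds ratio, each with a 95% interval.

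The adverse event tables also show the number and percentage of patients with each event. SAP 6.14, 6.14.2 and 6.14.6 refer to compound-level safety standards for more detail, including the kinds of summaries for special topics.

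Protocol 8.4.4.2 designates conjunctivitis, herpes infection or zoster, and parasitic or intracellular infection as events of special interest. Protocol 1.3.1.1 reports allergic conjunctivitis in "8 of 156 patients [5.1%] vs. 0% in placebo treated patients", and herpes or zoster in 6 of 156 lebrikizumab patients and no placebo patients. Protocol 1.3.1.3 reports: "The incidences of conjunctivitis (2.6% all lebrikizumab groups, 0 placebo), herpes infections (2.2% all lebrikizumab groups, 0 placebo".

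**The concern.** Both placebo-controlled Phase 2 studies in atopic dermatitis showed the same pattern for conjunctivitis and herpes: a few percent on lebrikizumab and none on placebo. The stated outputs serve that pattern poorly. A Fisher test on 150 and 75 patients has little power at such rates. An odds ratio with no placebo events has a zero denominator. The row would then show two percentages, a p-value above 0.05 and no usable effect estimate, and nothing would tell the reader how large an excess the data still allow.

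The caution in SAP 6.14 concerns reading too much into small p-values from data-driven hypotheses. It does not address the opposite error, reading a large p-value as reassurance.

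**Working it through.** **Inputs.** Arm sizes 150 and 75 (protocol 9.12). Two-sided Fisher exact test at 0.05 (SAP 6.1.2 and 6.14). Event rates from protocol 1.3.1.1 to 1.3.1.3. Assumptions: all patients dosed; Phase 2 rates carry over; true placebo rate 0% unless stated.

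**Method.** Power is the sum, over all outcomes (x, y) with Fisher p<0.05, of Binomial(x; 150, p1) × Binomial(y; 75, p2).

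**The plan's own figure first.** Protocol 9.12 states power above 95%. The enumeration gives 98.4% for IGA 0/1 (38% vs 13%) and 99.99% for EASI-75 (58% vs 20%), so the stated figure is reproduced.

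**Threshold with no placebo events.** 8/150 vs 0/75 gives p=0.054 and 9/150 vs 0/75 gives p=0.031. At least 9 lebrikizumab events are needed (9/150 = 6.0%). When p2=0, power is therefore P(X≥9) with X ~ Binomial(150, p1).

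| Event (source) | Rate vs 0% | Power | Miss probability |
|---|---|---|---|
| Allergic conjunctivitis (GS29250) | 5.1% | 36% | 64% |
| Herpes or zoster (GS29250) | 3.8% | 12% | 88% (87% with 6/156 unrounded) |
| Conjunctivitis (DRM06-AD01) | 2.6% | 1.7% | 98% |
| Herpes (DRM06-AD01) | 2.2% | 0.6% | 99% |

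Zoster alone in DRM06-AD01 (0.9% vs 0) would be missed almost always.

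**If the placebo rate is not zero.** At 5.1% vs an assumed 1%, power is 18%, a miss of 82%. The chance of no placebo events is then 0.99^75 = 47%.

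**Commoner imbalances, same method.**
- Drug-related events, DRM06-AD01, 16.2% vs 5.8%: miss 40%.
- Upper respiratory infection, GS29735 (open label, TCS comparator), 14.3% vs 3.7%: miss 30%.
- Skin infection, GS29735, 17.9% vs 7.4%: miss 44%.
- Any adverse event, GS29735, 64.3% vs 37.0%: miss 3%.

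**Odds ratio.** With x events on lebrikizumab and 0 on placebo it is (x × 75) / ((150 − x) × 0), which has no finite value.

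**What an interval adds.** For 4/150 vs 0/75, p=0.30. The risk difference is 2.7 points, with a 95% interval of −2.3 to +6.7 (Miettinen-Nurminen) or −2.5 to +6.7 (Newcombe). For 8/150 vs 0/75 it is 5.3 points, with an upper limit of 10.2 by either method. The lower limit depends on the method: above zero by Miettinen-Nurminen (+0.4), just below by Newcombe (−0.2).

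**The case against.** Several points on the other side stand.

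- The SAP defers to compound-level standards that were not available. They may already specify intervals or zero-cell rules. What can be said is that this SAP states none, not that none will be produced.
- A reader might infer that the flag misses 64% to 99% of all harms. The documents do not support that. The range is a miss probability for each of four selected events at an assumed placebo rate of exactly 0%, and other Phase 2 imbalances would be missed far less often.
- A reader might also infer that an inestimable odds ratio is the most likely result. That needs a placebo rate near zero; at 1%, zero placebo events has probability 47%. The Phase 2 evidence is 0 events in 54 and in 52 placebo patients, with one-sided 95% upper limits of 1 − 0.05^(1/54) = 5.4% and 1 − 0.05^(1/52) = 5.6%.
- The Phase 2 rates are pooled over several regimens, most of them not the one used here.
- The p-value is not the only safety information. Counts and percentages appear by arm. Conjunctivitis and infections also get follow-up-form characterisation and listings, and a safety monitoring board reviews cumulative data.
- Low power comes from the sample size, and an interval does not cure it. The interval for 4 vs 0 is itself inconclusive.

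These points narrow the finding but do not remove it. A percentage in each arm does not show how large a difference remains compatible with the data, and the SAP already uses intervals for that purpose on the efficacy side. A reader might also link the loss of patients at the excluded site to the mITT Population; for safety the relevant set is the Modified Safety Population, with the full Safety Population kept as a sensitivity analysis.

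**Conclusion.** The point holds as a gap in what this SAP states. Its between-arm safety comparison is a Fisher p-value flagged at 0.05 plus an odds ratio, with no interval and no zero-cell rule. For conjunctivitis and herpes, at pooled Phase 2 rates of 2.2% to 5.1% and an assumed placebo rate of 0%, the flag misses each event with probability 64% to 99%. When placebo has no events, fewer than 9/150 on lebrikizumab will not be flagged, and the odds ratio has no finite estimate whatever the lebrikizumab count (if above zero).

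This rests on 150 and 75 dosed patients and on Phase 2 rates carrying over to this regimen. A smaller Modified Safety Population would raise the miss probability: with an assumed 140 and 70, the miss at 5.1% is 71%. The documents do not show that the SAP treats p≥0.05 as evidence of no difference; the problem is that nothing in it guards against that reading. This is an inexpensive improvement in reporting and does not put the efficacy conclusions in question.

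**What to change.** In SAP 6.1.2, 6.14.2 and 6.14.6:

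1. For the events of special interest, the adverse event overview and the common TEAE rows, report the risk difference (lebrikizumab minus placebo) with one pre-named 95% interval valid at zero counts, for example Miettinen-Nurminen. If the compound-level standards already require this, cite the place.
2. State the upper 95% limit for each event of special interest.
3. Keep the Fisher p-value as a secondary flag, and show the odds ratio only when it can be estimated.
4. Add to 6.14 that p≥0.05 will not be described as absence of a difference, and reconcile the strong-evidence label with the caution that follows it.

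The cost is wording and one or two table columns, with no new data, patients or visits and no effect on the efficacy alpha. The drawbacks are wider tables, intervals not adjusted for multiplicity, and an occasional row where the interval and the Fisher p-value disagree. Naming one interval method in advance, and extending the existing caution to intervals, deals with most of that.
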